6.4 STATISTICAL TESTS

Unless otherwise indicated, all testing of statistical significance will be 2-sided, and a difference resulting in a p-value of <0.05 will be considered statistically significant.

6.5 COMMON CALCULATIONS

For quantitative measurements, change from baseline will be calculated as:

Value at Visit X – Baseline Value

Percent change from baseline will be calculated as:

$$\frac{\text{Value at Visit X} - \text{Baseline Value}}{\text{Baseline Value}} \times 100.$$

6.6 SOFTWARE VERSION

All analyses will be conducted using SAS version 9.4 or higher.

7. STATISTICAL CONSIDERATIONS

7.1 ADJUSTMENTS FOR COVARIATES AND FACTORS TO BE INCLUDED IN THE ANALYSIS

For details on the inclusion of the covariates in the models, see the specific analysis sections [16.1](#), [16.2](#), and [16.3](#).

7.2 MULTICENTRE STUDIES

This study will be conducted by multiple investigators at multiple centers in the United States.

Noven Pharmaceuticals, Inc.

Protocol HP-5000-US-07

Data from all sites will be pooled and statistical analyses will not be adjusted for investigational site.

7.3 MISSING DATA

The total and subscale scores of any assessment with more than one item, will be derived from individual items. Any individual missing item in any scale will not be imputed. If one or more items are missing at a visit, then the associated total score or subscale score will be set to missing.

Missing WOMAC scores will be imputed and used in sensitivity analyses of the primary and key secondary efficacy as per [section 16.1.4](#) and [16.1.5](#).

7.4 MULTIPLICITY ISSUES

For handling multiplicity in this study, a fixed-sequence procedure will be applied for primary and key secondary endpoints, where the order in which the hypotheses are tested is pre-specified as following: (1) WOMAC pain score, (2) WOMAC physical function score, and (3) WOMAC stiffness score. Testing begins with the first hypothesis about WOMAC pain score, and each test is carried out as long as a significant result with a level of significance of $\alpha=0.05$ is observed in all preceding tests. The fixed-sequence procedure controls the family-wise error rate because, for each hypothesis, testing is conditional upon rejecting all hypotheses earlier in the sequence.

All statistical tests of hypotheses in this analysis will be 2-sided with a Type I Error rate of 0.05.

7.5 ACTIVE CONTROL STUDIES INTENDED TO SHOW NON INFERIORITY OR EQUIVALENCE

Not applicable for the study.

7.6 EXAMINATION OF SUBGROUPS

Subgroup analyses will be performed for the primary endpoint on the ITT set. It should be noted that the study is not designed to detect treatment differences within subgroups.

The following subgroups may be assessed and described within the exploratory analysis section; however, categories for sub-grouping will be confirmed further based on empirical data:

- Age: (<65, 65 - <=75, >75), or data driven groups

Noven Pharmaceuticals, Inc.

Protocol HP-5000-US-07

Statistical Analysis Plan

Page 21 of 58

- Sex: Male/Female
- Race: As per data collected in the CRF
- Body mass index (BMI): (<18.5, 18.5 to <25.0, 25.0 to <30, >= 30.0)
- Severity: (Kellgren-Lawrence grade) of target knee based on X-ray before baseline
- Average and Worst NRS of Target Knee: (5 – 7 = moderate, 8 – 10 = severe) at baseline
- Contralateral Knee Involvement: (Yes/No)

8. OUTPUT PRESENTATIONS

The table, listing, and figure (TLF) shells provided with this SAP describe the presentations for this study and therefore the format and content of the summary TLFs to be provided by [REDACTED] Biostatistics.

Continuous variables will be summarized using descriptive statistics (number of subjects [n], mean, standard deviation [SD], median, minimum, and maximum, unless otherwise stated). The minimum and maximum will be reported to the same number of decimal places as the raw data recorded in the database. The mean and median will be reported to one more decimal place than the raw data recorded in the database. The SD will be reported to two more decimal places than the raw data recorded in the database.

Categorical variables will be summarized using frequency counts and percentages. Unless otherwise stated, the calculation of percentage will be based on the number of subjects in the analysis set of interest.

All p-values will be presented to four decimal places. P-values less than 0.0001 will be presented as "<0.0001". Unless otherwise indicated, all testing of statistical significance will be 2-sided, and a difference resulting in a p-value of <0.05 will be considered statistically significant. Confidence intervals (CIs) will be presented to two more decimal places than the raw data.

Source data for summary tables and statistical analyses will be presented as subject data listings.

Noven Pharmaceuticals, Inc.

Protocol HP-5000-US-07

9. DISPOSITION AND WITHDRAWALS

The numbers of subjects who are randomized, completed study treatment, discontinued from study treatment, and withdrew from the study, along with reasons for withdrawal will be tabulated overall and by treatment group for each analysis set. The withdrawal reasons will be presented under three categories: "study treatment related", "not study treatment related", and "uncertain". The specific reasons will be categorized under those three.

The number of subjects in each analysis population will be reported.

9.1 PROTOCOL DEVIATIONS

Protocol deviations are any changes to, deviations, or departures from the study design or procedures that are under the investigators' control and that have not been reviewed and approved by the Institutional Review Board (IRB) / Independent Ethics Committee (IEC).

Critical deviations are deviations from protocol-related procedures that threaten integrity of data, adversely affect subjects and/or could invalidate acceptability of a study (or part of it). Major deviations are unapproved changes or deviations from protocol-related procedures that could affect integrity, completeness, accuracy, and reliability of the data or adversely affect subject's rights, safety, or well-being. Minor deviations are deviations from accepted procedures that will not adversely affect subjects or data integrity.

The clinical lead will provide an excel file which includes all the critical, major, and minor deviations for each type along with a flag if the deviation was COVID-19 related to the biometrics team. The statistical programmer will use this file to create an analysis dataset.

Randomized subjects with major and minor protocol deviations will be listed. For the ITT Set, protocol deviations will be summarized by deviation criterion, treatment group, and overall. The deviation criterion has three levels critical, major, and minor. The number of subjects enrolled in error will also be summarized by treatment group and overall. Information indicating if the deviation is COVID-19 related will be listed.

10. DEMOGRAPHIC AND OTHER BASELINE CHARACTERISTICS

Demographic data and other baseline characteristics will be presented for the SAF Set. No formal statistical testing will be carried out for comparing demographic or other baseline characteristics between treatment groups.

Noven Pharmaceuticals, Inc.

Protocol HP-5000-US-07

The following demographic characteristics will be presented in summary tables and listings:

Age and age categories (< 65, 65 - ≤75, > 75)
Sex
Race
Ethnicity
Height (cm)
Weight (kg)
BMI (kg/m²)
BMI by category (kg/m²) (<18.5, 18.5 to <25.0, 25.0 to <30.0, ≥ 30.0)
Age at the onset of OA of the knees (years)

The following baseline characteristics will be presented:

Target knee (left or right)
NRS pain average (target knee) by category (mild: < 5, moderate: ≥ 5 to < 7, severe ≥ 7)
Is the diagnosis bilateral (Y/N)?
Kellgren-Lawrence grade for the target knee (0-4)
WOMAC pain score
WOMAC stiffness score
WOMAC physical function score
WOMAC composite score
NRS average pain score (target and non-target knee)
NRS worst pain score (target and non-target knee)
NRS average pain score frequency counts
NRS worst pain score frequency counts
WOMAC pain score by category (0 – 4, 5 – 8, 9 – 12, 13 – 16, 17 – 20)

11. MEDICAL HISTORY

Medical History information will be presented for the ITT Set. Medical History will be coded using Medical Dictionary for Regulatory Activities (MedDRA) currently in effect at the time of final database lock.

Any medical condition or clinically significant laboratory abnormality with an onset date after signing the ICF and before the time of dosing is considered to be pre-existing and should be documented as Medical History (and not as an AE). Pre-existing diseases or conditions will NOT be considered AEs unless there is an increase in the frequency or severity, or a change in the

 Noven Pharmaceuticals, Inc.

Protocol HP-5000-US-07

nature of the disease or condition during the Double-blind Treatment Phase.

The number and percentage of subjects with at least one pre-existing medical condition, as collected in the *Medical History* eCRF pages will be summarized by system organ class (SOC), preferred term (PT), treatment group, and overall.

Additionally, similar data will be summarized for prior surgeries, procedures, or therapies as collected in the *Surgeries, Procedure or Therapies* eCRF page, where the reason ticked is “Medical History”.

12. CONCOMITANT SURGERIES, PROCEDURES OR THERAPIES

Concomitant surgeries, procedures, or therapies will be presented for the SAF set. Each of these surgeries, procedures, or therapies will be categorized as either medical history that worsened during treatment or an AE per the definitions given in [section 11](#) and [section 18.1](#), respectively.

‘Concomitant’ surgeries, procedures, or therapies are those that:

- started on or after the date of first dose of study medication, which is the first patch application time, and started prior to the date of last dose of study medication, which is patch removal of past patch applied.
- AND stopped on or after the date of first dose of study medication or were ongoing at the completion of Week 12 post-dose assessments visit (or last treatment day which is removal of patch for subjects who discontinue treatment), or after the last dose of study medication (if planned assessments are not performed).

See [Appendix 1](#) for handling of partial dates, if it is not possible to define a surgery, procedure, or therapy as prior, prior and concomitant, concomitant, or post-treatment, it will be classified by the worst case (i.e., concomitant).

13. PRIOR AND CONCOMITANT MEDICATIONS

Prior medications will be presented for the ITT Set and concomitant medications will be presented for the SAF Set. Medications will be captured on the *Concomitant Medications* eCRF page and coded using the World Health Organization (WHO) Drug dictionary (WHODDE01SEPT2020 or later version).

‘Prior’ medications are medications which started and stopped prior to the date of first dose of

Noven Pharmaceuticals, Inc.

Protocol HP-5000-US-07

Statistical Analysis Plan

Page 25 of 58

study medication which is time of first patch application.

‘Concomitant’ medications are medications that:

- started on or after the date of first dose of study medication, which is the first patch application time, and started prior to the date of last dose of study medication, which is patch removal of past patch applied.
- AND stopped on or after the date of first dose of study medication or were ongoing at the completion of Week 12 post-dose assessments visit (or last treatment day which is removal of patch for subjects who discontinue treatment), or after the last dose of study medication (if planned assessments are not performed).

See [Appendix 1](#) for handling of partial dates for medications, if it is not possible to define a medication as prior, prior and concomitant, concomitant, or post-treatment, the medication will be classified by the worst case (i.e., concomitant).

Prior and concomitant medications will be summarized separately by treatment group, Anatomical Therapeutic Chemical (ATC) Level 2 and Standardized name (preferred term). All prior and concomitant medications will be listed flagging prior medication as “yes/no”.

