### 9.10.3 Concomitant Medication Cautions

Investigator's clinical judgment will be used in the following situations (the Medical Monitor for the study may be contacted if necessary);

- Angiotensin-converting enzyme (ACE) inhibitors, angiotensin receptor blockers (ARB) or beta-blockers: Concomitant use with HP-5000 may diminish the antihypertensive effect of these drugs. Monitor blood pressure.
- ACE Inhibitors and ARBs: Concomitant use with HP-5000 in elderly, volume depleted, or those with renal impairment may result in deterioration of renal function. In such high risk subjects, monitor for signs of worsening renal function.
- Diuretics: NSAIDs can reduce natriuretic effect of furosemide and thiazide diuretics. Monitor subjects to assure diuretic efficacy including antihypertensive effects.
- Digoxin: Concomitant use with HP-5000 can increase serum concentration and prolong half-life of digoxin. Monitor serum digoxin levels.

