Known	Known	
If stop date < study med start date, assign as prior
 
If stop date \geq study med start date and start date < study med start date, assign as prior concomitant
 
If stop date \geq study med start date and start date \leq end of treatment, assign as concomitant
 
If stop date \geq study med start date and start date > end of treatment, assign as post study

	Partial	
Impute stop date as latest possible date (i.e. last day of month if day unknown or 31st December if day and month are unknown), then:
 
If stop date < study med start date, assign as prior
 
If stop date \geq study med start date and start date < study med start date, assign as prior concomitant
 
If stop date \geq study med start date and start date \leq end of treatment, assign as concomitant
 
If stop date \geq study med start date and start date > end of treatment, assign as post study

	Missing	
If stop date is missing could never be assumed a prior medication
 
If start date \leq end of treatment, assign as concomitant
 
If start date > end of treatment, assign as post treatment

[REDACTED]

[figure not shown]
Noven Pharmaceuticals, Inc.

Protocol HP-5000-US-07

Statistical Analysis Plan

Page 53 of 58

START DATE	STOP DATE	ACTION
Partial	Known	
Impute start date as earliest possible date (i.e. first day of month if day unknown or 1st January if day and month are unknown), then:
 
If stop date < study med start date, assign as prior
 
If stop date \geq study med start date and start date < study med start date, assign as prior concomitant
 
If stop date \geq study med start date and start date \leq end of treatment, assign as concomitant
 
If stop date \geq study med start date and start date $>$ end of treatment, assign as post study

	Partial	
Impute start date as earliest possible date (i.e. first day of month if day unknown or 1st January if day and month are unknown) and impute stop date as latest possible date (i.e. last day of month if day unknown or 31st December if day and month are unknown), then:
 
If stop date < study med start date, assign as prior
 
If stop date \geq study med start date and start date < study med start date, assign as prior concomitant
 
If stop date \geq study med start date and start date \leq end of treatment, assign as concomitant
 
If stop date \geq study med start date and start date $>$ end of treatment, assign as post study

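### SAP Section 13 restricts concomitant medications to those started on or after first patch application, which contradicts Appendix 1 and leaves the place of continuing background drugs in the summaries unsettled

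*SAP*

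**What the plan says.** SAP Section 13 defines prior medications as "medications which started and stopped prior to the date of first dose of" study medication. Concomitant medications must meet two conditions. The first is that they "started on or after the date of first dose of study medication, which is the first patch application time", with a start before the last dose. The second is "AND stopped on or after the date of first dose of study medication or were ongoing at the completion of Week 12 post-dose assessments visit", with a variant for subjects who stop early.

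The two groups are then tabulated: "Prior and concomitant medications will be summarized separately by treatment group". Prior medications are presented on the ITT Set and concomitant medications on the SAF Set. All are listed, with a yes/no flag for prior.

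For partial dates Section 13 refers to Appendix 1. It adds that "if it is not possible to define a medication as prior, prior and concomitant, concomitant, or post-treatment", the worst case applies, meaning concomitant. So it names a class that is both prior and concomitant, but neither defines that class nor places it in a table.

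Appendix 1 also covers complete dates. With both dates known, a stop on or after first dose "and start date < study med start date, assign as prior concomitant". With the stop date missing, the rule is "If stop date is missing could never be assumed a prior medication", and the drug is concomitant if it started on or before end of treatment.

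SAP Section 12 uses the same start condition for concomitant surgeries, procedures and therapies.

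**The concern.** Background therapy is what a concomitant-medication table usually has to show, and the start condition in Section 13 shuts it out. The protocol expects such therapy: Section 9.10.1 permits drugs needed for ongoing conditions. Section 9.10.3 singles out ACE inhibitors, ARBs, beta-blockers, diuretics and digoxin. Of the first three it warns: "Concomitant use with HP-5000 may diminish the antihypertensive effect of these drugs. Monitor blood pressure". It also asks for attention to renal function in high-risk subjects on ACE inhibitors or ARBs.

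A programmer who follows Section 13 as written would produce a concomitant table holding only drugs newly started on treatment. A reader weighing blood-pressure or renal findings by arm would then see no background use of the named interaction drugs in it. A programmer who follows Appendix 1 would produce a different table. At stake is which medications the SAF concomitant summary counts, and whether two competent programmers would count the same ones.

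**Working it through.** The documents give no figure to reproduce, so the check is to apply both sets of rules to the same start and stop patterns.

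**Inputs.** S is the day of first patch application and E the day of last patch removal. For illustration S = 0 and E = 84, the Week 12 target day.

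**Section 13 rules.**
- Prior: start < S and stop < S.
- Concomitant: S ≤ start < E, and (stop ≥ S or ongoing).

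**Appendix 1 rules, start and stop known.**
- stop < S: prior.
- stop ≥ S and start < S: prior concomitant.
- stop ≥ S and start ≤ E: concomitant.
- stop ≥ S and start > E: post study.

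**Appendix 1 rules, start known and stop missing.**
- start ≤ E: concomitant.
- start > E: post treatment.

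**Results.**

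| Pattern (start, stop day) | Section 13 | Appendix 1, conditions met |
|---|---|---|
| Stopped before first patch (−100, −5) | prior | prior |
| Long-standing, no stop date (−1000, missing) | neither | concomitant |
| Long-standing, stopped on treatment (−1000, 30) | neither | prior concomitant; concomitant |
| Long-standing, stopped after treatment (−1000, 90) | neither | prior concomitant; concomitant |
| New on treatment (10, 20) | concomitant | concomitant |
| New on treatment, no stop date (10, missing) | concomitant | concomitant |
| Started on day of last removal (84, 86) | neither | concomitant |
| Started after treatment (88, 90) | neither | post study |

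**What follows.**

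1. The two rules disagree on all three patterns with start < S and use continuing past S. Section 13 gives no class; Appendix 1 always gives one.
2. The Section 13 wording looks like a drafting error. If start ≥ S, then stop ≥ start ≥ S, or the drug is ongoing, so the second condition excludes nothing. It does work only if drugs started before S were meant to qualify.
3. Within Appendix 1, the same long-standing drug changes class according to whether it has a stop date, although it was taken on treatment either way.
4. The known-date conditions overlap. Any start < S also satisfies start ≤ E. Stopping at the first match gives 'prior concomitant'; letting later lines overwrite earlier ones gives concomitant.
5. The SAP text sends prior and concomitant to summaries. It does not say where 'prior concomitant' is counted.
6. There is a small boundary mismatch as well: Section 13 requires a start before the last dose, while Appendix 1 accepts a start on the last day.

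**The case against.** The best defence is that Appendix 1 is the working algorithm and Section 13 a loose summary of it. Appendix 1 opens with complete dates, so it is not limited to partial ones, and it leaves no continuing drug unclassified. A chronic drug with no stop date becomes concomitant and reaches the SAF table. Section 13 itself names the overlap class and has a worst-case rule pointing to concomitant. The table shells that SAP Section 8 says accompany the plan, which are not among the documents reviewed, may settle the rest.

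Much of this stands, and it rules out stronger readings that a reader might infer:

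- **That all continuing drugs fall into neither safety summary.** This holds only if Section 13 is read without the appendix it cites. The prior table is also on the ITT Set, so it is not strictly a safety summary.
- **That the report could not show exposure to interacting drugs.** Protocol 13.4.4.3 requires every medication recorded in the eCRF to be listed, and calls for prior and concomitant summaries on the Safety population.
- **That prohibited analgesics carried into treatment would go unseen.** Breach of the washout restrictions is an exclusion criterion, and SAP 9.1 summarises protocol deviations by treatment group.

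The defence does not remove the contradiction. Section 13 sends the reader to Appendix 1 for partial dates only, while stating its own different rule for complete ones. The worst-case rule applies when a class cannot be determined. A drug with complete dates can be classed as 'prior concomitant', so the rule does not clearly reach it. The overlapping conditions and the missing table assignment remain.

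**Conclusion.** The point holds as a contradiction between SAP Section 13 and Appendix 1, together with a 'prior concomitant' class that has overlapping conditions and no stated summary. The Section 13 rule is wrong as written, and Section 12 carries the same start condition.

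The consequence is limited to the descriptive medication and therapy summaries. No efficacy result, hypothesis test or listing changes. Within those summaries the effect could be visible, because the concomitant table either includes or omits background drugs depending on the rule programmed.

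The number of subjects affected cannot be stated: the documents report no medication use. That most users of the drugs in protocol 9.10.3 began them before Day 0 is an assumption, plausible for long-term therapy in subjects aged 40 to 85 but not documented. That ongoing use is recorded as a missing stop date is also an assumption. If it is, Appendix 1 places those drugs in the concomitant table, and the drugs left without a stated summary are those with a known stop on or after first dose.

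**What to change.** - **SAP 13.** Define concomitant as taken at any time from first patch application to last patch removal, whatever the start date. Keep prior as stopped before first application.
- **'Prior concomitant'.** State that these medications are counted in the SAF concomitant summary, with the prior flag set to yes.
- **Appendix 1.** Make the conditions mutually exclusive. Treat the missing-stop rows the same way, so that a drug started before first application and continued gets the same class and flag whether or not a stop date is recorded.
- **SAP 12.** Align the definition, keeping the link to SAP 11, which separately summarises procedures and therapies recorded as medical history.

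The cost is SAP wording and a small change to one derivation, ideally made before unblinding. No new data are needed.
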